### 6.3 SUBJECT SETS ANALYSED

The following patient sets are defined

- *Screened Set (SCR)*  
Consists of all patients screened for the trial, with informed consent given and who completed at least one screening procedure at Visit 1.
- *Randomised set (RS)*  
This patient set includes all randomised patients, whether treated or not.
- *Treated set (TS)*  
This patient set includes all patients who were dispensed study medication and were documented to have taken at least one dose of investigational treatment.
- *Treated Set-Follow-up (TS-FU)*  
All patients in the TS, for whom a follow-up visit was performed (i.e. values of planned assessments- KCCQ, EQ-5D, vital signs or lab data reported) between 23 and 45 days after last intake of study medication.

The TS-FU does not include patients, where no planned measurements were taken, which may happen in case of telephone FU visits. Patients with intake of open label SGLT-2 inhibitor between their EOT and FU visit are also excluded from the TS-FU set.

- *Pharmacokinetic Set (PKS)*  
This patient set includes all evaluable patients of the treated set who provide at least one observation for at least one further PK endpoint of Cpre,ss,N for empagliflozin.

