## 7. PLANNED ANALYSIS

For End-Of-Text (EoT) tables, the set of summary statistics is: N / Mean / SD / SE / Min / Q1 (lower quartile)/ Median / Q3 (upper quartile)/ Max. The 1st and 99th percentiles might be substituting minimum and maximum in tables with open-ended values to safeguard against implausible extremes.

Geometric means and ranges will be added to the presentation or replace the presentation of mean and standard deviation for parameters which rather follow a log-normal distribution than a normal distribution.

Statistical parameters will be displayed to a defined number of decimal places as specified in the BI guideline “Reporting of Clinical Trials and Project Summaries” (4)

Tabulations of frequencies for categorical data will include all possible categories and will display the number of observations in a category as well as the percentage (%) relative to the respective treatment group (unless otherwise specified, all patients in the respective patient set whether they have non-missing values or not). Percentages will be rounded to one decimal place. The category missing will be displayed only if there are actually missing values.

Disposition of the patient population participating in the trial will be analysed by treatment groups and presented in the clinical trial report as a frequency-distribution.

Disposition as required for reporting for the trial in EudraCT will be provided. Enrolment will be summarised by country and by age group for reporting in EudraCT. (see (13)).

Number of patients lost to follow up (no information on vital status after start of study closure) and number of patients lost to follow up for the primary endpoint (no information on primary endpoint after start of study closure) will be summarised.

The reason for not randomising screened patients will be summarized descriptively.

The frequency of patients with IPDs will be presented by treatment group for the randomised set. The frequency of patients in different analysis sets will also be analyzed for each treatment group.

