Change from baseline in clinical summary score for HF symptoms and physical limitations domains of the KCCQ at week 52 will be evaluated by a mixed model for repeated measures (MMRM) including age (continuous) and  $eGFR (CKD-EPI)_{cr}$  at baseline (continuous) as linear covariates and, baseline score by visit, visit by treatment, sex, geographical region, baseline LVEF, and status of diabetes at baseline as fixed effects. An additional factor of “week reachable” for the parameter in question, which for each patient is the theoretically reachable planned measurement based on the time of randomisation will adjust for the different planned study times.

All on-treatment data up to week 52 will be included and the analysis will be conducted on the treated set.

A sensitivity analysis will be conducted including data after discontinuation (OC-AD) on the randomized set.

An additional analysis will be performed for the Clinical Summary Score on OC-AD without imputing a worst score for patients who die.

- *Occurrence of all-cause hospitalisation (first and recurrent)*

A similar joint frailty model as well as negative binomial regression model as in the HHF will be analysed for all-cause hospitalization. Instead of CV death, all-cause mortality will be jointly modelled as the terminal events in the joint frailty model.

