### Continuous endpoints:

The following endpoints will be evaluated by mixed models repeated measures (MMRM) as defined in the protocol.

- HbA1c change from baseline over time (OC-AD on the randomised set and OC-OT on the treated set)
- SBP, DBP change from baseline over time (OC-AD on the randomised set and OC-OT on the treated set)
- Weight change from baseline over time (OC-AD on the randomised set and OC-OT on the treated set)

- NT-pro BNP relative change from baseline over time (OC-AD on the randomised set and OC-OT on the treated set) (value will be transformed to the log scale before MMRM analysis. Estimates obtained from the model will then be back-transformed and reported on the original scale.)
- KCCQ overall summary score change from baseline at week 52 (OC-AD on the randomised set and OC-OT on the treated set) (model will include all timepoints up to week 52)
- KCCQ individual domains change from baseline at week 52 (OC-AD on the randomised set and OC-OT on the treated set) (model will include all timepoints up to week 52)
- KCCQ total symptom score change from baseline at week 52 (OC-AD on the randomised set and OC-OT on the treated set) (model will include all timepoints up to week 52)
- KCCQ based on patient-preferred outcome change from baseline at week 52 (OC-AD on the randomised set and OC-OT on the treated set) (model will include all timepoints up to week 52)
- UACR relative change from baseline over time (OC-AD on the randomised set and OC-OT on the treated set) (value will be transformed to the log scale before MMRM analysis. Estimates obtained from the model will then be back-transformed and reported on the original scale.)
- eGFR (CKD-EPI)cr change from baseline over time (OC-AD on the randomised set and OC-OT on the treated set)

As outlined in the protocol, the above endpoints will be analysed in a mixed model with repeated measures (MMRM), including age and eGFR (CKD-EPI)cr at baseline as linear covariates and visit by treatment interaction, baseline by visit interaction, geographical region, sex, baseline LVEF and status of diabetes at baseline as fixed effects. An additional factor of “week reachable” for the parameter in question, which for each patient is the theoretically reachable planned measurement based on the time of randomisation will adjust for the different planned study times.

An unstructured covariance structure will be used to model the within-patient errors.

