For an evaluation of follow-up after discontinuation of trial medication an additional summary of the NT-proBNP, FG, eGFR, UACR, creatinine and the KCCQ endpoints as above will be produced. This summary will include descriptive statistics for baseline, actual values and change from baseline to last on-treatment value and follow-up, and change from last on-treatment assessment to follow-up. The TS-FU patient set will be the basis for this summary, but only those patients with a valid baseline, last value on treatment and follow-up value will be included in all displays. Analyses will be repeated for patients with at least 52 weeks of cumulative exposure (excluding treatment gaps). FG analysis will also be conducted by DM status at baseline (3 categories).

Analyses of change from baseline to LVOT and FU on the TS-FU outlined above will be additionally modelled, separately for LVOT and FU. An analysis of covariance (ANCOVA) model including treatment group, sex, geographical region, baseline LVEF and status of diabetes at baseline as fixed effects and baseline eGFR (CKD-EPI)cr (continuous), age (continuous), and baseline of the endpoint (if not already included) as linear covariates will be used.

In addition to the ANCOVA models described above, descriptive statistics will be presented also for creatinine for the value at visit and change from baseline based on OC-AD on the randomised set and OC-OT on the treated set.

In addition to the analyses defined above, KCCQ clinical summary score, clinical symptoms and physical limitations domain will be analysed in two responder analyses (1) defining an increase of 5 points or more from baseline as improvement and (2) defining a reduction of 5 points or more as deterioration.

The frequency and percentage (relative to RS) of patients with improvement as well as the frequency and percentage of patients with deterioration will be described. Patients lost to follow-up or who withdrew consent prior week 52 as well as patients who died prior week 52 will be considered as having a deterioration (no improvement) in KCCQ.

Improvement and deterioration will be analysed in separate logistic regression models including treatment, age (continuous), eGFR (CKD-EPI)cr at baseline (continuous), region, sex, baseline LVEF (categorical), status of diabetes at baseline, and baseline value of the KCCQ domain analyzed.

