## **9.6 DETERMINATION OF SAMPLE SIZE**

The trial is designed to achieve a power of 90% for a two-sided test with  $\alpha=0.05$  and hazard ratio 0.80. To achieve this at least 841 patients with a primary event are required.

Including the interim analysis with Hwang, Shih and De Cani  $\alpha$ -spending function at 60% information with parameter  $\gamma = -8$  will diminish the power only slightly to 89.98%.

The drop-out rate from the trial is assumed to be very low (<1% per year) and is not considered for determination of sample size.

A 15% yearly event rate in the placebo group is assumed. Assuming an accrual period of 18 months and a follow-up period of 20 months, it was planned to randomise 2850 patients to accrue 841 events.

The event rate and recruitment progress is assessed in a blinded manner during recruitment before any interim unblinding. If the accumulated blinded data suggests a slower accrual of primary outcome events over calendar time than originally projected, then the number of randomised patients may be increased to a maximum of 4000 patients. Operationally, the recruitment period would be extended and could continue up to 6 months before the target number of events is expected to be achieved. The number of confirmed primary outcome events will not be affected by this consideration and will remain 841 events.

While continuously monitoring the event rate in the above described manner, it is currently planned to include approximately 3600 patients in this trial.

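### KCCQ responder percentages are taken over all randomised patients, including any closed out before a week-52 score is possible, so they depend partly on when recruitment stops

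*SAP*

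**What the plan says.** SAP section 7.6, under the continuous endpoints, adds two responder analyses of the KCCQ clinical summary score and related domains: a gain of at least 5 points is improvement, a fall of at least 5 points is deterioration. The denominator is stated for improvement: "The frequency and percentage (relative to RS) of patients with improvement". The parallel wording for deterioration names none, but the general rule in SAP section 7 counts "all patients in the respective patient set whether they have non-missing values or not", so the same denominator is implied. SAP section 6.3 defines the randomised set without any follow-up condition: "This patient set includes all randomised patients, whether treated or not".

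Week 52 enters only through the rule for patients without a score. "Patients lost to follow-up or who withdrew consent prior week 52 as well as patients who died prior week 52" count as deteriorated and not improved. No other reason for lacking a week-52 score is mentioned. The covariates of the two logistic models are listed, and none concerns planned follow-up time.

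Elsewhere the SAP does recognise unequal planned follow-up. The KCCQ mixed model in section 7.5.2 carries a factor that is the "theoretically reachable planned measurement based on the time of randomisation will adjust for the different planned study times", and the mixed models in section 7.6 use the same factor. SAP section 9.6 explains why follow-up can be short: if events come slowly, recruitment "could continue up to 6 months before the target number of events is expected to be achieved", and about 3600 patients are now planned against 2850 at the outset.

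**The concern.** A patient randomised late, still in the trial and closed out as planned before the week-52 window, has no week-52 KCCQ. The responder rule gives this patient no outcome, yet the denominator rule keeps the patient in. Such a patient cannot be counted as improved, and can be counted as deteriorated only through death, loss or withdrawal. The reported percentages and their difference then depend on how close to trial end recruitment stopped, which has nothing to do with treatment or with how patients fared. They would also not describe the same patients as the KCCQ mixed models, which adjust for reachable follow-up. In addition, the logistic models can be programmed in two ways from the same text: these patients coded as non-events, or dropped.

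**Working it through.** **Inputs.** 841 events, HR 0.80, 15% yearly placebo rate, 18 months' accrual plus 20 months' follow-up, 2850 patients originally, about 3600 now, at most 4000 (Protocol 7.7, SAP 9.6). Interim at about 500 events (Protocol 7.4). Week-52 KCCQ window: days 296 to 435 (SAP Table 6.7:1). KCCQ is also collected at the end-of-treatment visit (Protocol flow chart), so a form completed at close-out from day 296 counts as week 52. *Assumed:* uniform accrual, exponential event times, 30.44 days per month, no lag between reaching the event target and close-out.

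**Reproducing the plan.** With placebo hazard λ = −ln(0.85), accrual A and minimum follow-up F in years:

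P(event) = 1 − [exp(−λF) − exp(−λ(A+F))]/(λA).

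For A = 1.5 and F = 20/12 this is 0.323 on placebo and 0.268 on active (hazard 0.8λ), mean 0.296. Then 841/0.2958 = 2843 patients, against 2850 stated. Schoenfeld's formula gives 845 events against 841. The model matches the design.

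**Share that cannot reach week 52.** Share = (months needed − minimum follow-up)/accrual months, floored at 0. Months needed: 296/30.44 = 9.72 by the SAP window; 364/30.44 = 11.96 by nominal week 52.

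| Scenario | Accrual (months) | Minimum follow-up (months) | Share, day-296 window | Share, nominal week 52 |
|---|---|---|---|---|
| 2850, original plan | 18 | 20 | 0% | 0% |
| 3600, original recruitment rate (2850/18 = 158 per month) | 22.7 | 10.8 | 0% | 5.3% |
| 4000, original recruitment rate | 25.3 | 7.1 | 10.4% | 19.3% |
| 3600, last patient 6 months before 841 events | 32.8 | 6 | 11.3% (about 408) | 18.1% (about 653) |
| 4000, last patient 6 months before 841 events | 27.6 | 6 | 13.5% (about 541) | 21.6% (about 865) |
| 2850 in 18 months, stopped at 500 events | 18 | 7.0 | 15.1% | 27.5% |

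Example, fourth row: (9.72 − 6)/32.8 = 11.3%. In the 6-month rows the accrual length is solved so that 841 events fall 6 months after the last randomisation. With other placebo rates in those two rows, the day-296 share is 6.5% to 7.5% at 10% per year and 15.2% to 18.4% at 18% per year.

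**Effect on the results.** If f is the unreachable share, an outcome that needs a week-52 score is reported as its rate among reachable patients × (1 − f). The rates of 40% and 35% below are illustrative and not from the documents.

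| f | Reported improvement | Difference (points) | OR, coded as non-events | OR, left out |
|---|---|---|---|---|
| 0 | 40.0% v 35.0% | 5.0 | 1.24 | 1.24 |
| 11.4% | 35.4% v 31.0% | 4.4 | 1.22 | 1.24 |
| 13.5% | 34.6% v 30.3% | 4.3 | 1.22 | 1.24 |
| 21.6% | 31.4% v 27.4% | 3.9 | 1.21 | 1.24 |

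The ratio of the two percentages stays at 40/35 = 1.14 in every row.

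**The case against.** Much of the case against stands. Six months is a permitted limit on late recruitment, not a planned minimum, so a reader might infer that many patients will be affected, but the documents do not say so. The original design leaves nobody short, and 3600 patients at the original rate leave nobody short by the SAP's own window.

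A reader might also reckon 25% or 33% from 24 or 18 months' accrual with 6 months' minimum follow-up. Those scenarios do not fit the design: at the 4000-patient cap they give about 775 and 661 events, and reaching 841 would take about 4338 and 5090 patients. They also use a 12-month threshold, which ignores the day-296 window.

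It is tempting to call this a bias in the treatment comparison. It is not differential: reachability depends on randomisation date, which 1:1 randomisation should balance. Nor can one say that the logistic result is pulled to the null, since that depends on coding the SAP leaves open. Deterioration is diluted less than improvement, because deaths, losses and withdrawals among late recruits still count. The analysis lies outside the testing hierarchy, and the main week-52 KCCQ analysis is the mixed model, which already adjusts.

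These arguments limit the size and importance of the point. They do not supply the missing rule, and the stated denominator still gives a calendar-dependent percentage.

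**Conclusion.** The point holds as a low-priority defect of specification. The share of the randomised set that cannot have a week-52 KCCQ is 0% to about 14% at the final analysis by the SAP's window, or up to about 22% by nominal week 52. After an interim stop under the original accrual plan it would be about 15% (27.5% nominal). These figures rest on uniform accrual, a 15% placebo rate, HR 0.80 and no close-out lag; any lag lowers them, and a different event rate shifts them as shown. Improvement percentages and the absolute difference shrink by that share and deterioration by less, similarly in both arms. The odds ratio moves by 0.02 to 0.03 in the illustration, or not at all, depending on coding that the SAP does not state. No confirmatory conclusion is affected.

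**What to change.** Before database lock, add one or two sentences to SAP section 7.6:

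- For both improvement and deterioration, the denominator of the percentages and the population of the logistic models are the randomised patients for whom the week-52 KCCQ window was reachable.
- Reachability is judged from the randomisation date and the planned close-out date, using the Table 6.7:1 window (day 296 onward). A 365-day cut-off should not be used, because it would discard valid week-52 scores from patients closed out between days 296 and 364.
- Death, loss to follow-up and consent withdrawal before week 52 remain deterioration within that set.

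The version over all randomised patients can be kept as a sensitivity analysis, with a statement of how unreachable patients are coded.

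The cost is small. The mixed models already need a reachability variable, and because it depends only on calendar dates the randomised comparison is preserved. The downside is a slightly smaller analysis set.

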#### Win ratio:

An unmatched win ratio considering adjudicated CV death and adjudicated HHF will be analysed based on unmatched pairs. All patients randomised to empagliflozin will be compared to all patients randomised to placebo. Only common follow-up time will be considered for the comparison. Patients on empagliflozin are considered to have “won” the comparison if either the other patient has died due to CV causes while the patient on empagliflozin was still alive, or if both patients did not die due to CV causes, then if the other patient had more occurrences of HHF, or if the number of occurrences of HHF is the same but the time to the first occurrence of HHF is longer. The number of comparisons won is noted as  $N_w$ . Patients on empagliflozin are considered to have “lost” the comparison if the empagliflozin patient died due to a CV cause while the patient on placebo was still alive, or if both patients did not die due to a CV cause, then if the patient on empagliflozin had more

occurrences of HHF, or if the number of occurrences is the same but the time to the first occurrence of HHF is shorter for the empagliflozin patient. The number of comparisons lost is noted as  $N_L$ . The win ratio is  $N_W/N_L$ .

The rules for winning and losing follow a modified Rogers 2014 (8) approach also considering the time to the first HHF event in case of a tie on the number of HHF events. The analysis of the unmatched win ratio will be conducted as described in Pocock 2012 (11).

#### Other types of further endpoints

For other types of endpoints e.g., occurrence of adjudicated HHF within 30 days after first adjudicated HHF, change in NYHA class at week 52, HCRU and EQ-5D, descriptive statistics will be provided.

For NYHA class a shift table will also be provided for changes from baseline over time and for change from baseline to last value on treatment and last value in study and worst value in study.

The number of patients shifting from normal (no pre-diabetes) to pre-diabetes or diabetes as well as shifts from pre-diabetes to diabetes will be summarized.

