5.1.3 Further endpoints

- Time from first to second adjudicated HHF
- Time to first all-cause hospitalisation
- Occurrence of adjudicated HHF within 30 days after first adjudicated HHF
- Occurrence of adjudicated HHF and CV death. This endpoint will account for clinical hierarchies in composite outcomes, i.e. CV death is ascribed greater importance than HHF (see win ratio in [Section 7.3.3](#))
- New onset of atrial fibrillation
- Adjudicated MI (fatal or non-fatal)
- Adjudicated stroke (fatal or non-fatal)
- Adjudicated TIA
- Composite of time to first event of all-cause mortality and all-cause hospitalisation
- Composite of adjudicated CV death or adjudicated non-fatal MI
- Composite of adjudicated CV death or adjudicated non-fatal stroke
- Adjudicated CV death, adjudicated non-fatal MI, adjudicated non-fatal stroke (3-point MACE)
- Progression to macro albuminuria (defined as UACR >300 mg/g) from baseline for patients with baseline UACR ≤ 300 mg/g
- Time to first new onset of sustained normo- or micro-albuminuria (UACR ≤ 300 mg/g) in patients with macro albuminuria at baseline
- Time to first new onset of sustained normo-albuminuria (UACR < 30 mg/g) in patients with micro- or macro-albuminuria at baseline
- eGFR (CKD-EPI)_{cr} change from baseline to 30 days after treatment stop
- Composite of sustained reduction of ≥40% eGFR (CKD-EPI)_{cr} or sustained eGFR(CKD-EPI)_{cr} <15 mL/min/1.73 m² (< 10 mL/min/1.73 m² for patients with eGFR (CKD-EPI)_{cr} <30 mL/min/1.73 m² at baseline) or adjudicated CV death
- Composite of sustained reduction of ≥40% eGFR (CKD-EPI)_{cr} or sustained eGFR(CKD-EPI)_{cr} <15 mL/min/1.73 m² (< 10 mL/min/1.73 m² for patients with eGFR (CKD-EPI)_{cr} <30 mL/min/1.73 m² at baseline) or all-cause mortality
- Composite of sustained reduction of ≥40% eGFR (CKD-EPI)_{cr} or sustained eGFR (CKD-EPI)_{cr} <15 mL/min/1.73 m² (< 10 mL/min/1.73 m² for patients with eGFR (CKD-EPI)_{cr} < 30mL/min/1.73 m² at baseline), adjudicated CV death, or adjudicated HHF
- Change from baseline in KCCQ overall summary score at week 52
- Change from baseline in KCCQ total symptom score at week 52
- Change from baseline in KCCQ individual domains at week 52

- Change from baseline in KCCQ based on patient-preferred outcome at week 52
- Change in NYHA class from baseline at week 52
- Change from baseline in Health-related quality of life measured by EQ-5D
- Health economic analysis by Health Care Resource Utilisation (HCRU)

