7.3.3 Further endpoint analyses

Further time-to-event endpoints will be analysed in the same Cox proportional hazards model as the primary analysis.

Change from baseline to 30 days after treatment stop of eGFR (CKD-EPI)_{cr} will be evaluated by an ANCOVA model, including treatment group, gender, geographical region, baseline LVEF, and history of DM as fixed effects and baseline eGFR (CKD-EPI)_{cr} (continuous) and age (continuous) as linear covariates.

An unmatched win ratio considering adjudicated CV death and adjudicated HHF will be analysed based on unmatched pairs. All patients randomised to empagliflozin will be compared to all patients randomised to placebo. Only common follow-up time will be considered for the comparison. Patients on empagliflozin are considered to have “won” the comparison if either the other patient has died while the patient on empagliflozin was still alive, or if both patients did not die, then if the other patient had more occurrences of HHF, or if the number of occurrences of HHF is the same but the time to the first occurrence of HHF is longer. The number of comparisons won is noted as N_W . Patients on empagliflozin are considered to have “lost” the comparison if the empagliflozin patient died while the patient on placebo was still alive, or if both patients did not die, then if the patient on empagliflozin had more occurrences of HHF, or if the number of occurrences of HHF is the same but the time to the first occurrence of HHF is shorter. The number of comparisons lost is noted as N_L . The win ratio is N_W / N_L .

The rules for winning and losing follow a modified Rogers 2014 [[R16-4909](#)] approach also considering the time to the first HHF event in case of a tie on the number of HHF events. The analysis of the unmatched win ratio will be conducted as described in Pocock 2012 [[R16-4813](#)].

Further longitudinal continuous endpoints will be analysed in a mixed model with repeated measures (MMRM), including age and eGFR (CKD-EPI)_{cr} at baseline as linear covariates and visit by treatment interaction, baseline by visit interaction, geographical region, gender, baseline LVEF, and baseline history of DM as fixed effects.

The details of analyses will be defined in the TSAP prior to unblinding.

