7.5 HANDLING OF MISSING DATA

There will be no imputation for safety data or for time-to-event type of endpoints. For patients who discontinue the trial treatment prematurely, all efforts will be made to follow the patients for survival and any other endpoints, including the primary and key secondary endpoints, until the end of the trial.

For the slope analysis of eGFR (CKD-EPI)_{cr}, all available on-treatment change from baseline data will be used. Patients without on-treatment data after randomisation will not be included in this analysis.

For the analysis of change from baseline to 30 days after treatment stop, only available data will be used. Only patients with post-treatment data will be used in this analysis.

For other longitudinal efficacy endpoints such as KCCQ scores, MMRM methodology will be used. Models will be run on both all observed data and all observed on-treatment data. Details of the imputation rule will be given in the statistical analysis plan.

An eGFR (CDK-EPI) reduction is considered sustained, if it is determined by two consecutive post-baseline central laboratory measurements separated by ≥ 30 days. If only one post-baseline value is available and the patient dies within 60 days of this measurement without second measurement ≥ 30 days after the first, then the eGFR reduction is also considered sustained.

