#### 4. CHANGES IN THE PLANNED ANALYSIS OF THE STUDY

1. In the random coefficient model used to estimate slope in change from baseline of eGFR (CKD-EPI)cr, an additional fixed effect term of interaction of eGFR (CKD-EPI)cr at baseline (continuous) by time is included.
2. As per protocol the objective of the trial is “to demonstrate superiority of empagliflozin 10 mg versus placebo”.  
The ITT analysis approach was chosen to as closely as possible reflect real-life conditions, disregarding any occurrences of treatment stop or restart of treatment, that may happen in clinical practice as well.  
However, it is also recognized and recommended by the Steering Committee that the study-specific treatment discontinuation in the close-out period does not resemble clinical practice.  
Therefore for patients that complete the treatment period according to protocol after close-out announcement the time at risk for efficacy endpoints ends at the discontinuation of treatment and events occurring thereafter are not considered in the efficacy analyses.  
The primary estimand is now specified in [Section 7.4](#).  
An analysis including all events after randomization will be conducted as sensitivity analysis for the primary endpoint and the key secondary endpoint of recurrent HHF. A corresponding approach will be used for continuous endpoints.
3. Mixed model for repeated measures (MMRM) for KCCQ at week 52 as well as other MMRMs were specified in condensed form to be in line with BI internal standards. Therefore, individual model terms were removed from the MMRM if already included as interaction term with treatment or visit. Additionally, the terms included in MMRMs were aligned throughout the TSAP
4. The rules defining ‘win’ and ‘lose’ for the win ratio calculation were clarified and adapted to also consider the time to first HHF event in case of a tie in the number of HHF events. The adaption was made since time to first HHF event is also considered relevant information to avoid ties in case the number of HHF events is identical. This approach is a modification of the rules applied by Rogers 2014 ([8](#)).

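### EQ-VAS change from baseline has no prespecified baseline-adjusted treatment difference: the SAP keeps EQ-5D descriptive where the protocol's general rule calls for an MMRM, and does not record the departure

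*SAP*

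**What the plan says.** Protocol 5.1.3 lists "Change from baseline in Health-related quality of life measured by EQ-5D" as a further endpoint, on a separate line from resource use (HCRU). It names neither a visit nor a score. The flow chart schedules EQ-5D at Visit 2, at weeks 12, 32, 52, 100 and 148, at end of treatment and at follow-up. Protocol 5.6.1 describes two parts: five dimensions with five levels each, and a self-rated scale from 0 to 100.

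Protocol 7.3.3 gives the general rule: "Further longitudinal continuous endpoints will be analysed in a mixed model with repeated measures (MMRM". The model includes baseline by visit, visit by treatment, age, baseline eGFR, region, gender, LVEF and diabetes history. Protocol 7.5 adds "For other longitudinal efficacy endpoints such as KCCQ scores, MMRM methodology will be used", with models run on all observed data and on on-treatment data. Section 7.3.3 ends: "The details of analyses will be defined in the TSAP prior to unblinding".

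In SAP 7.6, the list of continuous endpoints for MMRM contains HbA1c, blood pressure, weight, NT-proBNP, UACR, eGFR and the KCCQ scores, but not EQ-5D. Under other types of further endpoints the SAP says "change in NYHA class at week 52, HCRU and EQ-5D, descriptive statistics will be provided". For summary tables, SAP Section 7 states that "the set of summary statistics is: N / Mean / SD / SE / Min / Q1", followed by median, upper quartile and maximum.

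**The concern.** The EQ-VAS is a continuous score measured at baseline and at several later visits, so it fits the protocol's MMRM rule. Every other repeatedly measured continuous change from baseline listed in Protocol 5.1.3 gets an MMRM in the SAP; pulse rate gets its MMRM in SAP 7.8.3. The EQ-VAS is the exception, and no reason is given.

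What is at stake is a planned treatment difference, with interval, that uses the baseline value already collected. A model added after unblinding would be post hoc. An MMRM would also use partial follow-up under a missing-at-random assumption, which arm-by-arm visit summaries do not.

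**Working it through.** **1. Does the rule reach this endpoint?**

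| Part of EQ-5D | Longitudinal? | Continuous? | Covered by Protocol 7.3.3? |
|---|---|---|---|
| EQ-VAS, 0 to 100 | yes | yes | yes, by its general wording |
| Five dimensions, five levels each | yes | no, ordinal | not clearly |
| Index score | not defined in either document | – | cannot be judged |

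The gap is therefore established for the EQ-VAS only.

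**2. Is the departure recorded?** SAP Section 4 has five items: the slope interaction, the end of time at risk, condensed MMRM terms, win-ratio rules and LVEF categories. None concerns EQ-5D. The SAP history table has no entry on it either.

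**3. Is there a figure in the plan to reproduce?** None exists for EQ-5D: no SD, correlation, precision or power is stated. The trial's sizing figure is 841 primary events at a hazard ratio of 0.80 (Protocol 7.7). Schoenfeld's formula gives 4(1.960 + 1.282)² / (ln 0.80)², which rounds up to 845, within 0.5% of 841. That figure is not affected by this point.

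**4. What would baseline adjustment gain?** Take one follow-up visit, equal variances at both times, and correlation ρ between baseline and follow-up. ANCOVA stands in for the MMRM. In units of 2·SD²/n, with n per arm, the variance of the treatment difference is:

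- raw change: 2(1 − ρ)
- baseline-adjusted: 1 − ρ²
- ratio, adjusted to raw change: (1 − ρ²) / [2(1 − ρ)] = (1 + ρ)/2

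The variance reduction is (1 − ρ)/2, and the reduction in SE or interval width is 1 − √[(1 + ρ)/2]. The values of ρ are assumptions. The half-widths use 1.96·√(variance × 2/n) with n = 1800, half of the roughly 3600 patients in SAP 9.6, and assume no missing data.

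| ρ (assumed) | Variance reduction | SE or CI-width reduction | 95% CI half-width in SD units, raw change → adjusted |
|---|---|---|---|
| 0.4 | 30% | 16% | 0.072 → 0.060 |
| 0.5 | 25% | 13% | 0.065 → 0.057 |
| 0.6 | 20% | 11% | 0.058 → 0.052 |
| 0.7 | 15% | 8% | 0.051 → 0.047 |
| 0.8 | 10% | 5% | 0.041 → 0.039 |

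At ρ = 0.5, for example, the ratio is 1.5/2 = 0.75. The variance falls by 25%, and the SE by 1 − √0.75 = 13%.

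**The case against.** The strongest reply is that the protocol never promised this model for EQ-5D. No MMRM sentence names it, the endpoint has no stated score or visit, and the details are left to the SAP. Protocol 5.6 groups EQ-5D with resource use under other assessments, and Protocol 5.7 gives health economic evaluation as the purpose of the quality-of-life questionnaires. Resource use is also listed in Protocol 5.1.3, and nobody expects an MMRM for it.

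Much of this stands. The obligation comes from a general rule, it clearly reaches only the EQ-VAS, and descriptive analysis may have been intended. A reader might infer that the SAP downgraded the analysis at a later revision. The documents do not support that: the history table shows no change to EQ-5D since the February 2017 version.

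Two things do not yield. Replacing a model by no model is more than a detail. And Section 4 does record a smaller MMRM matter, that the KCCQ model "as well as other MMRMs were specified in condensed form to be in line with BI internal standards", so an endpoint left outside the MMRM rule belongs there too.

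It is also fair to say that an MMRM does not by itself settle how deaths count. SAP 6.6.1 imputes a score of 0 after death for KCCQ only. The SAP also does not say which of its observed-case approaches applies to the EQ-5D summaries.

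**Conclusion.** The discrepancy is real, narrow and of low importance. The protocol's rule covers the EQ-VAS, the SAP gives it no model, and the departure is not recorded. What is missing is a prespecified baseline-adjusted difference with its interval.

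Three stronger readings are tempting, and the documents do not support them:

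- **That the trial loses its quality-of-life comparison.** KCCQ keeps its MMRM. For EQ-5D, the per-arm N, mean and SE allow an unadjusted difference and interval to be derived.
- **That 15% to 30% of precision is lost.** That range is a variance reduction, holds only for an assumed ρ of 0.7 down to 0.4, and corresponds to 8% to 16% in SE or interval width. At ρ = 0.8 it is 10% in variance and 5% in SE.
- **That power is lost.** The SAP plans no EQ-5D test and neither document states a power for it, so there is no baseline from which to measure a loss.

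The sizes rest on a one-visit approximation with equal variances and no missing data. They leave out any gain from other visits and covariates. EQ-5D is outside the testing hierarchy, so the type I error, the 841 events and the primary and key secondary results do not change.

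**What to change.** Before unblinding, add EQ-VAS change from baseline to the MMRM list in SAP 7.6. Use the terms already specified there: baseline by visit, visit by treatment, age, baseline eGFR, region, sex, LVEF category, diabetes status and the week-reachable factor. Run it as OC-AD on the randomised set and OC-OT on the treated set.

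State how scheduled visits after death are handled, because the KCCQ rule does not extend to EQ-5D. Keep the five dimensions and resource use descriptive, and add an index score only if one is defined. If descriptive analysis of the EQ-VAS was intended, the lesser alternative is to record that choice with its reason in SAP Section 4.

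The cost is a few lines of SAP text and one more run of an existing type of model. The 7-day on-treatment window for patient-reported outcomes (Table 6.1:2) and the visit-window algorithm (SAP 6.7) are already in place, and no new data are needed.
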